**Background:**

One major, yet poorly understood cardiovascular health risk that occurs in as many as 24% of males and 9% of females within the US population is obstructive sleep apnea (OSA). Severe OSA increases cardiovascular mortality 4 fold, and even when corrected for other risk factors increases cardiovascular mortality 3 fold. OSA can participate in both the initiation and progression of several cardiovascular diseases including sudden death, hypertension, arrhythmias, myocardial ischemia and stroke. Treatment of OSA is primarily continuous positive airway pressure (CPAP).

Diminished cardiac vagal activity is thought to be associated with many of the adverse cardiovascular consequences of OSA. Heart rate is dominated by cardioinhibitory parasympathetic activity. Parasympathetic cardiac vagal activity is typically cardioprotective and there is a high tonic level of parasympathetic and little sympathetic cardiac activity at rest. Re-establishment of cardiac vagal activity prevents arrhythmias, decreases risk of sudden death, and protects against ischemic/reperfusion injury, suggesting that restoring parasympathetic cardiac activity could be an effective therapeutic target to decrease mortality and morbidity associated with OSA.

In human volunteers intranasal administration of oxytocin significantly increases parasympathetic and decreases sympathetic cardiac control. In addition to the classic effects of oxytocin on uterine contraction and milk ejection, recent work indicates oxytocin is present in both males and females and has an important role in both behavior and cardiovascular homeostasis, particularly during anxiety and stress.

There are no clinical guidelines for the use of intranasal oxytocin in the treatment of sleep apnea but we propose that it may have a positive impact on the outcome of patients with sleep apnea, however, this research is not intended to change any clinical guidelines.

This project's specific aim will test the following hypothesis:

Intranasal oxytocin administration will blunt the deleterious hypoxia/hypercapnia induced changes in heart rate that occur during apnea in patients with OSA.

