**Study Proposal:**

This proposal, based on the above detailed role of oxytocin in increasing parasympathetic and decreasing sympathetic cardiac control, will test if oxytocin administration blunts the deleterious hypoxia/hypercapnia induced changes in heart rate that occur during apnea in patients with OSA. This project will lay the groundwork and provide preliminary data to obtain NM funding to test this hypothesis more thoroughly and in larger clinical trials.

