**Study Objectives:**

Primary Objective: This study will explore if intranasal oxytocin has any positive impact on blunting the deleterious hypoxia/hypercapnia induced changes in heart rate that occur during apnea in patients with OSA.

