#### **Cohort A: 10 Subjects**

1. 10 subjects that have recently undergone a standard "in the sleep-lab" diagnostic polysomnography (per standard of care medical guidelines, and not for research purposes) and have been diagnosed with OSA will be recruited into the research study to assess the beneficial effects of oxytocin treatment.
2. For research: These 10 subjects will undergo another "in the sleep-lab" diagnostic polysomnography that is identical to the one that they had for standard of care to diagnose OSA. This polysomnography that is performed for research will be funded externally by the investigating group.

*If subjects are female and of child bearing potential, then their birth control method for the duration of the study will be recorded, and a urine pregnancy test will be performed prior to the PSG.*

3. Within one hour prior to the research polysomnography the subjects will be given oxytocin 40 International Units, (IU) intranasally.
4. The following 4 outcome measurements will be compared between the two sequential diagnostic polysomnographies (initial without, and second with oxytocin) in the same subjects:
  - i. basal heart rate before sleep (primary outcome)
  - ii. mean changes in heart rate with apneic and hypopneic events (primary outcome)
  - iii. apnea-hypopnea index (secondary outcome)
  - iv. percentage of time spent by the patient with oxygen saturations: > 90%, > 80% but < 90%, and < 80% (secondary outcome)

The intranasal oxytocin dose is 40 IU. The drug will be stored in the Investigational Drug Pharmacy according to the vendor's recommendations.

Polysomnography (PSG) is a comprehensive recording of the biophysiological changes that occur during sleep. It is usually performed at night, when most people sleep, though some labs can accommodate shift workers and people with circadian rhythm sleep disorders and do the test at other times of the day. The PSG monitors many body functions including brain (EEG), eye movements (EOG), muscle activity or skeletal muscle activation (EMG) and heart rhythm (ECG) during sleep. After the identification of the sleep disorder sleep apnea in the 1970s, respiratory airflow and respiratory effort indicators were added, along with peripheral pulse oximetry.

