#### **Cohort B: 40 Subjects**

Once enrollment in Cohort A is complete, then enrollment into Cohort B will begin.

1. 40 Subjects that have recently undergone either a standard "in the sleep-lab" diagnostic polysomnography (per standard of care medical guidelines, and not for research purposes) or an "at home" PSG test and have been diagnosed with OSA will be recruited into the research study where we will assess the beneficial effects of oxytocin treatment.
2. For research: These 40 subjects will undergo an "in the sleep-lab" diagnostic polysomnography that would be identical to the one they had for standard of care medical guidelines if they were diagnosed with OSA "in the sleep-lab". This research

polysomnography should be performed within **4 weeks** of their OSA diagnosis PSG. This PSG that is being performed for research will be funded externally by the investigating group.

*If subjects are female and of child bearing potential, then their birth control method for the duration of the study will be recorded, and a urine pregnancy test will be performed prior to the PSG.*

3. Subjects will be randomized by the Investigational Drug Services Pharmacy of the MFA to be administered either Oxytocin (40 IU) or placebo within one hour prior to beginning the study polysomnography.
  - a. Both the polysomnography technician, the patient, and all research staff will be blinded to this randomization. The only un-blinded personnel will be the IDS pharmacy staff.
4. Subjects will then return within **4 weeks** to have a **second research study** polysomnography performed by the sleep-lab. This polysomnography that is being performed for research will be funded externally by the investigating group.
5. Subjects will be administered the intervention that *they did not receive* during the first research PSG study within one hour prior to beginning the second polysomnography. Either Oxytocin (40 IU) or placebo.
  - a. Both the polysomnography technician, the patient, and all research staff will be blinded to this randomization. The only un-blinded personnel will be the IDS pharmacy staff.

*For example: If at study polysomnography 1 a subject is randomized to receive placebo 1 hour prior to the start of the polysomnography, then at study polysomnography 2 the subject will be administered oxytocin (40 IU) 1 hour prior to the start of the polysomnography.*

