6. The following 4 outcome measurements will be compared between the two sequential diagnostic PSGs (initial standard of care without oxytocin, and second for research with oxytocin) in the same subjects:
  - i. basal heart rate before sleep (primary outcome)
  - ii. mean changes in heart rate with apneic and hypopneic events (primary outcome)
  - iii. apnea-hypopnea index (secondary outcome)
  - iv. percentage of time spent by the patient with oxygen saturations: > 90%, > 80% but < 90%, and < 80% (secondary outcome)

The intranasal oxytocin dose is 40 IU. The drug will be stored in the Investigational Drug Pharmacy according to the vendor's recommendations.

Polysomnography (PSG) is a comprehensive recording of the biophysiological changes that occur during sleep. It is usually performed at night, when most people sleep, though some labs can accommodate shift workers and people with circadian rhythm sleep disorders and do the test at other times of the day. The PSG monitors many body functions including brain (EEG), eye movements (EOG), muscle activity or skeletal muscle activation (EMG) and heart rhythm (ECG) during sleep. After the identification of the sleep disorder sleep apnea in the 1970s, respiratory airflow and respiratory effort indicators were added, along with peripheral pulse oximetry.

Inclusion Criteria:

- Men or women 18 years old or older of any ethnic background

- Subjects that have recently undergone a standard "in the sleep-lab" diagnostic polysomnography (per standard of care medical guidelines), or the "at home" diagnostic test for cohort B, and have been diagnosed with OSA will be recruited into a follow-up study to assess the beneficial effects of oxytocin treatment.

Exclusion Criteria:

- Pregnant or nursing women.
- Women at any child bearing age who are not willing to undergo pregnancy tests, and stable and reliable methods to prevent pregnancy
  - A female subject of childbearing potential is a non-menopausal female who has not had a hysterectomy, bilateral oophorectomy, or medically documented ovarian failure. Menopause can be assumed to have occurred in a woman when there is either:
    1. Appropriate medical documentation of prior complete bilateral oophorectomy  
OR

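### Two outcomes are labelled primary, but only the heart rate change with apneic events measures the stated hypothesis; basal heart rate should not lead, and the Cohort B comparison must be the randomized one.

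*Combined protocol and SAP*

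**What the plan says.** The specific-aim hypothesis in Background is: "Intranasal oxytocin administration will blunt the deleterious hypoxia/hypercapnia induced changes in heart rate that occur during apnea in patients with OSA". Study Objectives gives one objective with the same target: "This study will explore if intranasal oxytocin has any positive impact on blunting the deleterious hypoxia/hypercapnia induced changes in heart rate". Neither mentions resting heart rate.

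The outcome lists in Cohort A (item 4) and Cohort B (item 6) are identical. Outcome i is "basal heart rate before sleep (primary outcome" and outcome ii is "mean changes in heart rate with apneic and hypopneic events (primary outcome"; both carry the primary label. The apnea-hypopnea index and the oxygen saturation bands are secondary.

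Background supplies the reason for looking at basal heart rate: "In human volunteers intranasal administration of oxytocin significantly increases parasympathetic and decreases sympathetic cardiac control". Study Proposal sets the ambition: "This project will lay the groundwork and provide preliminary data".

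Statistical Considerations names ANOVA and Fisher's exact test and says that consulting a statistician will be considered. It gives no alpha, no order of testing, no success rule and no multiplicity rule.

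Cohort B items 3 to 5 describe a blinded, randomized crossover in which each subject has one research night on oxytocin and one on placebo. Item 6 then describes the comparison differently, as the initial standard-of-care night without oxytocin against a second, research night with it. Cohort A uses nearly the same description ("initial without, and second with oxytocin"), and there it fits the design.

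**The concern.** Basal heart rate is read before sleep, so it precedes every scored sleep-apnea event. It can show that oxytocin altered resting autonomic tone. It cannot show that the heart rate response to apnea was blunted.

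On the protocol's own reasoning, a fall in basal heart rate with no blunting is a plausible result. With two unranked primary outcomes and no success rule, such a result could be presented as a positive primary finding and carried into the case for larger trials, although the question posed had not been answered in the affirmative.

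The comparison in Cohort B item 6 makes this worse for either outcome. Taken literally, it leaves out the placebo night, which is what the randomization was for.

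**Working it through.** **1. Match each outcome to the aim.** The plan states no alpha, power, effect size or variance, so there is no figure of its own to reproduce. The main check is on the text.

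| Item | Target | Measures heart rate change during apnea? |
|---|---|---|
| Hypothesis (Background) | Heart rate change during apnea | – |
| Sole objective (Study Objectives) | Heart rate change during apnea | – |
| Outcome i, primary | Heart rate before sleep | No |
| Outcome ii, primary | Heart rate change with apneic and hypopneic events | Yes |

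No other section ranks the two or states a separate aim for outcome i.

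**2. Size under an either-outcome rule (illustrative).** Assumptions, none in the plan: each outcome is tested at two-sided 0.05, success on either counts, there is no effect on either, and the test statistics are bivariate normal with correlation ρ.

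- P(at least one false success) = 1 − P(|Z1| < 1.96 and |Z2| < 1.96).
- At ρ = 0: 1 − 0.95² = 0.0975.
- P(false success on basal heart rate only) = P(at least one) − 0.05, because outcome ii alone accounts for 0.05.

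| ρ | At least one | Basal only |
|---|---|---|
| 0 | 9.75% | 4.75% |
| 0.5 | 9.1% | 4.1% |
| 0.8 | 7.8% | 2.8% |
| 0.9 | 7.0% | 2.0% |

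If both outcomes must succeed, or if outcome ii is tested first, the figure does not exceed 5%.

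**3. Cost of each remedy.** Assume 80% power for each outcome at 0.05, with all 40 Cohort B subjects completing.

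- Even alpha split: with 38 degrees of freedom, the effect that has 80% power at 0.05 (about 0.45 SD of the within-subject difference) has 70.5% power at 0.025.
- Both must succeed: 0.80 × 0.80 = 64% at ρ = 0, rising to 75% at ρ = 0.9.
- Outcome ii tested first: 80% for outcome ii. A formal claim on basal heart rate needs both to succeed, so it has 64% to 75%, or at most 5% if there is no blunting.

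**4. The comparison in Cohort B.** Items 3 and 5 give every subject both interventions, in randomized order. Item 6 differs from this in three ways:

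- It uses the diagnostic night as the comparator, so placebo plays no part.
- It puts oxytocin on the second night, whereas items 3 and 5 have some subjects on placebo at the second research night.
- Item 1 admits subjects diagnosed by laboratory study "or an 'at home' PSG test". For the latter, item 6 would set a home recording against a laboratory one.

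**5. How outcome ii is summarized.** The documents give neither the direction of the change nor the event windows. Averaging the absolute size of each event's change may look like a neutral answer, but it turns noise into signal. If the true change is 0 and the event-level noise is normal with SD 4 (an assumed value), the mean absolute change is 4 × √(2/π) = 3.2. The signed mean is 0. A treatment that altered only heart rate variability would then shift the absolute measure with no change in the event response.

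**The case against.** The strongest reply is that the study is openly exploratory and rests on vagal tone. Pairing a marker of mechanism with a marker of event response is a defensible design for groundwork. Two primary outcomes are permissible, and a reader shown both results could see for themselves that only basal heart rate moved. The plan's silence on a success rule is also compatible with requiring both, or with estimation only.

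Much of this stands. Basal heart rate belongs in the study, and nothing here makes it an invalid measure. The error rates in the working belong to an either-outcome rule that the plan does not state. A reader might infer that the trial has an inflated type I error; the documents do not support that, because they specify neither an alpha nor a rule for claiming success, and they describe the purpose as preliminary.

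The mechanistic argument does not, however, turn basal heart rate into a measure of blunting during apnea, and no objective about resting heart rate is written down. An explicit objective would cure the mismatch as well as a change of label would. Nor does the exploratory purpose explain why item 6 drops the placebo comparison.

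**Conclusion.** The mismatch is certain on the text: two outcomes are labelled primary, and one of them cannot address the hypothesis or the sole objective. Its consequence is a risk of misinterpretation, to be considered and cheaply removed, and not a demonstrated failure of error control. The 7.0% to 9.75% range shows the scale only if each outcome is tested at two-sided 0.05, either may succeed, and the correlation lies between 0.9 and 0. The power figures also assume 80% power for each outcome, which no variance in the documents supports.

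The comparison in Cohort B item 6 is wrong as written. It contradicts the crossover in items 3 to 5 and, if followed, would discard the randomized placebo comparison.

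**What to change.** For Cohort B:

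- Name the mean heart rate change with apneic and hypopneic events as the primary outcome, tested first at two-sided 0.05.
- Make basal heart rate secondary, or test it at 0.05 only after the primary outcome succeeds. Report both with an estimate and 95% interval whatever the result.
- If the investigators want resting heart rate to carry equal weight, add an explicit objective for it, with a stated success rule and alpha control (an even split, or both must succeed), at the power cost shown.
- Replace the comparison in item 6 with oxytocin night versus placebo night, analysed within subject with research night and treatment in the model.
- Keep outcome ii as one signed mean per subject per night over the scored events. Before unblinding, fix the pre-event and event windows and the direction that counts as blunting. Do not average absolute event-level changes.

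Report Cohort A descriptively: it has 10 subjects, no placebo and a fixed order.

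The cost is a protocol amendment to the outcome lists, Cohort B item 6 and Statistical Considerations, plus one scoring rule applied to ECG and events that are already recorded. No further nights or subjects are needed. The downside is that, with outcome ii leading, basal heart rate alone can no longer make the study positive.

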    2. Permanent cessation of previously occurring menses as a result of ovarian failure with documentation of hormonal deficiency. Ovarian hormonal deficiency is documented by serum follicle stimulating hormone (FSH) level elevated to within the post-menopausal range based on the laboratory reference range where the hormonal assay is performed.  
OR
    3. Menopause is defined as occurring 12 months after your last menstrual period and marks the end of menstrual cycles
- Subjects who are on medications that affect cardiac autonomic function (eg. Beta blockers)
- Smokers
- Subjects who are unable to read or answer questions in the English language

The following information will be recorded on each patient before and after the use of intranasal oxytocin:

- Clinical data:
  1. Demographics — Age, gender, ethnicity, weight, BMI.
  2. Physiological data to be acquired:
    - a. Basal heart rate before sleep
    - b. Apnea-hypopnea index
    - c. Mean changes in heart rate with apneic and hypopneic events
    - d. Percentage of time spent by the patient with oxygen saturations: > 90%, > 80% but < 90%, and < 80%.
  3. Medical History Information: Current and past medical conditions, to be investigated for correlations to sleep.
  4. Standard of care sleep study data:
- The Polysomnography (PSG) monitors many body functions during sleep, including brain (EEG), eye movements (EGG), muscle activity or skeletal muscle activation (EMG), heart rhythm (ECG), respiratory airflow, thoracic and abdominal respiratory effort, body position, limb movement, and oxygen saturation using pulse oximetry. Recording and scoring is done per the standards set by the American Academy of Sleep Medicine.

All these data will be stored in a secured cabinet in the division of Pulmonary, Critical Care and Sleep Disorders offices. The primary investigator and study staff only will have access to these data. These data will lack any information that may lead to identifying any subject in the research.

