#### **Statistical Considerations:**

ANOVA and Fisher's Exact Test will be done to compare multiple means from repeated measures. A consultation with an expert statistician will also be considered for data analysis.

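### Do the oxygen saturation bands need rewording because readings of exactly 90% and exactly 80% fall in none of them?

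*Combined protocol and SAP*

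**What the plan says.** The saturation outcome is stated three times in the combined protocol and SAP, each time with the same cuts.

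- Cohort A, item 4 iv: "percentage of time spent by the patient with oxygen saturations: > 90%, > 80% but < 90%, and < 80% (secondary outcome".
- Cohort B, item 6 iv: "oxygen saturations: > 90%, > 80% but < 90%, and < 80% (secondary outcome".
- The list of physiological data after the exclusion criteria, item 2d: "Percentage of time spent by the patient with oxygen saturations: > 90%, > 80% but < 90%, and < 80".

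On measurement, the standard-of-care sleep study paragraph names "oxygen saturation using pulse oximetry" and adds: "Recording and scoring is done per the standards set by the American Academy of Sleep Medicine". It gives no resolution, rounding rule or averaging time. The Statistical Considerations section says "ANOVA and Fisher's Exact Test will be done to compare multiple means from repeated measures" and has no rule for readings that fall on a cut.

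**The concern.** All the printed signs are strict, so a reading of exactly 90% is neither above 90% nor between 80% and 90%, and a reading of exactly 80% has the same problem one cut lower. If the oximeter reports whole percents, 90% can be a common value in patients with sleep apnea, and a noticeable part of the night could go uncounted.

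Two consequences would follow. The three percentages would not total 100%, and whoever writes the summary might close the gap in their own way, so that the reported time in the upper band depended on an undocumented choice. A shift in saturation would also appear with different sizes in the upper and middle bands, because part of it would pass through the unassigned value. At stake is the clarity of one secondary outcome.

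**Working it through.** **Which values are left out.** The printed bands are S > 90, 80 < S < 90 and S < 80. Checking every value from 50 to 100 in steps of 1 and of 0.1 leaves exactly two values unassigned, 80 and 90, and puts none in two bands. With the cuts closed as S ≥ 90, 80 ≤ S < 90 and S < 80, every value falls in exactly one band.

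**How much time that could be.** The plan gives no figure to reproduce. The assumptions here are a normal overnight distribution with mean m and SD s, readings rounded to resolution r, and none above 100. The share at a reading c is

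[Φ((c + r/2 − m)/s) − Φ((c − r/2 − m)/s)] / Φ((100 + r/2 − m)/s).

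For m = 92, s = 3, r = 1, c = 90: [Φ(−0.500) − Φ(−0.833)] / Φ(2.833) = (0.3085 − 0.2023) / 0.9977 = 10.6%. Adding the trace at 80 gives 10.65%.

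| Mean / SD | Uncounted, r = 1 | Uncounted, r = 0.1 |
|---|---|---|
| 95 / 2 | 0.93% | 0.09% |
| 94 / 2.5 | 4.50% | 0.45% |
| 93 / 3 | 8.12% | 0.81% |
| 92 / 3 | 10.65% | 1.07% |
| 91 / 4 | 9.96% | 1.00% |
| 90 / 5 | 9.22% | 0.93% |
| 88 / 6 | 9.19% | 0.92% |

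These seven pairs are illustrations, not bounds. Mean 91, SD 3 gives 12.55% and 1.26%; mean 90, SD 2 gives 19.7% and 1.99%. Resolution alone changes the answer about tenfold.

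**Does the gap cause the mismatch between bands?** Take SD 3, r = 1 and a mean rising from 92 to 93. With the printed bands, time above 90% rises 10.6 points (69.1% to 79.6%) and the middle band falls 8.0. With closed bands both move 8.0. At r = 0.1 the printed bands give +9.45 and −9.20, a difference of 0.25 points. That example has almost no time below 80%. Where there is some, closing the bands does not restore symmetry. For SD 6, r = 1 and a mean rising from 88 to 89:

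| Bands | Upper | Middle | Lower |
|---|---|---|---|
| Printed | +5.8 | −3.5 | −2.2 |
| Closed | +6.2 | −4.0 | −2.2 |

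With three bands, the upper and middle need not mirror each other, because time also moves in and out of the lowest. The mismatch is mostly a property of having three bands.

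**Does it affect the comparison?** Time above 90% is a well-defined quantity, and so is time below 80%. Both cohorts compare studies within the same subjects using one printed set of cuts. A subject's uncounted time can differ between nights as saturation shifts, but each band still measures the same thing on both nights.

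**The case for a change.** The best case for a change is cost: three wording edits and one cut in the oximetry summary, with no new data, would remove a choice that can move a reported percentage. At mean 92, SD 3 with whole-percent readings, reporting > 90% gives 69.1% and reporting ≥ 90% gives 79.7%. Neither the scoring sentence nor the statistical section settles which. That stands as a description of the text, but it concerns the level reported, and a summary that prints its cut removes the ambiguity.

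A second argument is that Cohort B admits patients diagnosed by an at-home test, whose oximeter might have another resolution. If that recording were used, results could differ by device, but closing the bands would not cure this. At mean 92, SD 3, time at ≥ 90% with 0.1% readings is 1 − Φ((89.95 − 92)/3) / Φ((100.05 − 92)/3) = 1 − 0.2472/0.9964 = 75.2%, against 79.7% with whole-percent readings, a difference of 4.5 points. With the printed > 90% cut the figures are 1 − 0.2578/0.9964 = 74.1% and 69.1%, a difference of 5.0 points. The device difference is almost the same either way.

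Finally, identical strict signs in three places make an isolated slip less likely. They do not exclude a systematic loss of 'or equal' signs when the PDF was read, or wording copied from one place to the others.

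**Conclusion.** The observation is accurate as far as the printed text goes: exactly 90% and exactly 80% are in no band, and nothing else in the documents assigns them. No change to the plan is called for. The strict bands are valid threshold measures, the printed cuts are the same for every sleep study, no bias or loss of a treatment effect is shown, and the heart rate primary outcomes do not depend on saturation. An analyst building the oximetry summary would meet the boundary values at once and place each in one band.

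The size is undetermined. Under assumed normal distributions it runs from under 1% to about 20% of the night with whole-percent readings, and from about 0.1% to 2% with 0.1% readings. The conclusion rests on one cut being applied to all recordings compared, which is how the outcome is written, and not on those figures.
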